19.0 Investigator responsibilities	22
Appendices:.....	23

List of Abbreviations

AE	Adverse Event
CRF	Case report form
GEE	Generalized Estimating Equations
IRB	Institutional Review Board
KATH	Komfo Anokye Teaching Hospital
MOP	Manual of Procedures
N	Number (typically refers to number of participants)
NGO	Non-governmental Organization
PATH	PATH
PI	Principal Investigator
QA	Quality Assurance
QC	Quality Control
RA	Research Assistant
REDCap	Research Electronic Data Capture
SAE	Serious Adverse Event
SCH	Seattle Children's Hospital
SCRI	Seattle Children's Research Institute
UNICEF	United Nation's Children's Fund
UP	Unanticipated Problem
UW	University of Washington
V1, V2....V6	Visit 1, Visit 2 and so on
WHO	World Health Organization

1.0 Background and rationale for the study

We will establish an evidence base for the Nifty Feeding Cup by evaluating its effectiveness and caregiver satisfaction. We will conduct a randomized crossover trial that compares the Nifty Feeding Cup to a standardized, generic medicine cup used to feed preterm infants with breastfeeding difficulties at Komfo Anokye Teaching Hospital (KATH) in Kumasi, Ghana. This work has the potential to improve the health and survival of over 9 million infants born in South Asia and Africa.

1.1 The Nifty Feeding Cup Premise

The Nifty Feeding Cup (Figure 1) is a simple, safe, easy-to-clean, ergonomic, and affordable tool designed to optimize feeding and the efficient hand expression of breast milk to newborn preterm infants and other infants with breastfeeding difficulties. Its unique shape minimizes spillage, enables the infant to participate in the feed, is large enough for direct hand expression of breast milk, and its soft material minimizes injury to the infant's mouth and helps control flow. The Nifty Feeding Cup offers a standard cup for cup feeding infants in low resource settings where none currently exists.

Figure 1. Nifty Feeding Cup by Laerdal

1.2 Background and Context

Feeding devices used in high-resource settings for infants with breastfeeding difficulties such as nasogastric tubes, bottles, and breast pumps are impractical and unhygienic in settings that lack clean water and electricity.¹ The World Health Organization (WHO) and United Nations Children's Fund (UNICEF) recommend hand expression of breast milk and the use of a small cup to feed newborns with breastfeeding difficulties in low-resource settings.²⁻⁴

No standard feeding cup for these infants exists. Non-specific cups such as small shot glasses, medicine cups, the paladai (a 10-ml beaked cup used in south India), and generic drinking cups are used worldwide. Other tools used include spoons and syringes. Generic cups have several key disadvantages. Most cups have relatively wide rims that make it difficult for the mother to control the rate at which milk flows into a newborn's mouth and makes it difficult to maintain a constant bolus of milk to the infant at all times. Poor milk access and flow control decreases intake and lengthens feeding times which decreases net weight gain because of the excess energy it takes to feed. The risk of infection is higher because cups are often made of metal or hard plastic which often cuts the thin, tender skin surrounding the preterm newborn's mouth. Conventional cups are too small for hand expression of breast milk, which means breast milk is transferred from other, possibly contaminated containers prior to feeding to the newborn.

Cups are more easily sanitized than bottles and only require the infant be able to swallow and breathe, which demands less energy and skill than the more complex suck/swallow/breathe mechanism needed for breastfeeding.⁵ Preterm infants developing their suck-swallow-breathe mechanism often require supplemental feedings until they can exclusively breastfeed.⁶ In low-resource settings, an optimized cup is the best way to provide these supplement feeds. Appropriate cup feeding of a newborn is achieved by delivering milk to the edge of the infant's

mouth and enabling the infant to lap or sip the milk at her own pace in a calm manner that encourages rapid, optimal intake and promotes mother-infant bonding.

The wide rims on generic cups make it difficult for the inexperienced cup feeding and new mother to control the rate of milk flow to a newborn's mouth. Rapid or inconsistent rate of milk flow from wide-rimmed cups is an incorrect feeding pattern.⁷ This method results in spillage, stresses the infant, and often causes the infant to cough or aspirate which in turn reduces essential nutritional intake, increases feeding duration and fatigue, and frustrates the mother whose milk is laboriously hand expressed to only then be spilled and wasted. Over a short period of time, this type of feeding may quickly result in chronic insufficient caloric intake that reduces endurance and increases a vulnerable neonate's risk of undernutrition, failure to grow, infection, and death. For example, the difference between adequate and inadequate intake can be as little as 2 teaspoons per feed for a 33-week preterm infant weighing 1,800 grams.

The Nifty Feeding Cup (Figure 1) addresses this problem by use of the reservoir which makes a bolus of milk constantly available to the infant at all times and minimizes spillage. Similar to breastfeeding, this allows the infant to participate in the feed by controlling how much milk is taken in and allows them to coordinate their suck, swallow, breathing during the feeding cycle. Minimizing spillage preserves precious hand expressed breast milk.

The original NIFTY Cup was designed by a team of investigators from Seattle Children's Hospital, PATH and the University of Washington. Since 2015, we have also collaborated with Laerdal Global Health, our industrial partner, on the design. We conducted formative research on the Nifty Feeding Cup design in neonatal intensive care units in hospitals in India and Tanzania. An iterative design process was employed incorporating feedback from testing to improve the design. The cup was well received. In some design tests we compared the NIFTY™ to the paladai, a small beaked cup used widely in South India. Mothers and lactation providers preferred the NIFTY Cup to the paladai because of: 1) less spillage, 2) fewer cuts to the mouth, and 3) its larger size. Because we have not widely tested the NIFTY Cup in Africa and because there is no uniformity in cups used, we will conduct the Nifty Feeding Cup clinical trial with partners in Ghana.

In sum, we propose the Nifty Feeding Cup will improve the feeding experience of the mother-infant pair and will become the standard cup for feeding infants with breastfeeding difficulties in low resource settings.

1.3 Justification

Generic cups are subpar at feeding infants with breastfeeding difficulties in low resource settings. We expect the Nifty Feeding Cup to succeed because it is specifically designed to optimize intake, reduce feeding spillage, duration, and infection risk. We posit it will decrease cup feeding problems, and improve the caregiver's experience of cup feeding her infant. A better cup for feeding infants with breastfeeding difficulties is needed. The Nifty Feeding Cup will fill this need.

1.4 Significance

Little attention has been given to feeding newborns with breastfeeding difficulties yet the potential impact is huge. There are over 9 million preterm infants and other infants with potential breastfeeding difficulties (e.g. craniofacial anomalies, orphans) born each year in Africa and South Asia. These infants are at high risk of death and malnutrition. Safe, early, frequent, and sufficient nutrition is an essential component of helping these babies grow, develop and survive. This will be the first comparative study of the Nifty Feeding Cup and the first research study of the Nifty Feeding Cup in Africa. Given the large numbers and the ramifications of poor early feeding, this study has the potential for global impact.

2.0 Study objectives

2.1 Goal and Objective

The goal is to establish an evidence base for the Nifty Feeding Cup and to evaluate its effectiveness and patient caregiver satisfaction. Our objective is to conduct a randomized crossover trial that compares the Nifty Feeding Cup to a standardized, generic cup used to feed preterm infants with breastfeeding difficulties at KATH in Kumasi, Ghana.

2.2 Aim and Hypotheses

We aim to compare the Nifty Feeding Cup to a standardized, generic cup in up to 200 caregivers and their preterm infants. We will test the hypotheses that Nifty Feeding Cup feeding compared to generic cup feeding will result in:

Primary:

1. Less spillage.
2. Greater caregiver satisfaction

Secondary:

3. Greater intake of milk (accounting for spillage, exploratory)
4. Shorter feeds (exploratory)
5. Greater caregiver satisfaction 4 weeks post-discharge

Our aim and hypotheses were selected based on the most informative outcomes given the scope of the funding. The above hypotheses are framed in terms of the statistical alternative which is typically more intuitive to non-statisticians.

2.3 Statistical Justification

Power for this study was determined by our primary hypotheses for the study H_A 1 related to amount of spillage and H_A 2 related to intake of milk. With 150 (up to 200) pairs, we estimate we will be able to detect at least a 5% difference in spillage or intake with 90% power and an alpha of 0.05 if no design effects are present. Carryover effects occur when a participant learns from cup feeding with the first cup which then affects the outcomes when feeding with the second cup. We will be able to statistically evaluate if carryover effects are present. If carryover effects are observed, we will have 80% power to detect an average 5% difference in spillage or intake.

These estimates are based on studies report differences in intake and spillage.⁸⁻¹⁰ We used the ‘power’ command in Stata 13.0 to estimate power using a two-sided paired t-test. We selected a conservative difference based on other studies, which showed differences between 6.3 and 7.8ml.⁸⁻¹⁰ We used a published estimate of a cup feeding standard deviation of 11¹⁰ and conservative correlations ranging from 0.02 to 0.5. This power calculation is also applicable to a 5% difference caregiver satisfaction between the two cups.

3.0 Study design

We will conduct a randomized crossover trial in mothers/caregivers with a preterm infant in the mother-baby unit at Komfo Anokye Teaching Hospital (KATH) in Kumasi, Ghana. Each caregiver/infant pair will use the Nifty Feeding Cup for about 24 to 36 hours and the standardized generic cup for about 24 to 36 hours. Cross-over means each caregiver/infant pair will use both cups, with the order of the cup used first and second randomized. See Section 8 for further description of study products.

3.1 Statistical Analysis

The data analyst will be blinded to the cup assignment. We will use generalized estimating equations for a crossover design to assess intake, spillage, and feeding duration and a sign test to assess the caregiver’s preference. Covariates may include factors such as amount of prior feeding, type of nutrition, number of prior cup feeds with assigned cup, and number of cup feeds between measured feedings. Most covariates typically accounted for (maternal age, other demographics) will not be included because the comparison is the same caregiver/infant pair.

We will conduct exploratory analyses stratifying on age (0-14 days and 15-28 days) and gestational age (<34 weeks and 34-36 weeks) to evaluate potential effect modification by these factors. These are exploratory since this study was not powered to detect effect modification. For each cup separately, we will compare estimates for those assigned the cup first to estimates for those assigned the cup second to evaluate for design effects. If design effects are observed we will analyze our data comparing those first assigned the Nifty cup to those first assigned to the medicine cup, dropping the data from the second cup and removing the cross over design from our study. We will use Stata 13.0 for all statistical analysis. Consistent with our power calculations, a two-sided p-value of 0.05 will be used.

A strength of our statistical approach is that participants with outcome data for at least one feeding assessment are able to be included in our GEE analyses even if other time points are missing. We will evaluate the potential effect of other missing data on our associations using multiple imputation methods.¹²

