5.1.3 Visit 3. Cup 1 Feed 2 (Day 1, >2 hours after V2)

The RA will measure a second feeding at V3. There may or may not be feedings between V2 and V3. During Visit 3, the RA will:

- Conduct the Feeding Assessment
- Remove Cup 1 so it is not inadvertently or preferentially used over Cup 2
- Provide the caregiver with Cup 2 and the instructions for use.

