5.2.2 Outcomes

Outcomes related to intake, spillage, and duration will be measured at each Feeding Assessment, which will take place at Visit 2 through 5. Caregiver satisfaction will be measured during Feeding Assessment related to the experience of that feed (V2-V5). Caregiver satisfaction will be measured with the In-Hospital Preference Survey (V5) and the Follow-up Survey (V6).

Milk Intake. We will measure amount (in ml) and weight (in grams) of milk in the cup before the feeding. We will measure the amount and weight of milk in the cup after the feeding. If the cup is refilled, we will measure the amount and weight before and after the refill. The amount and weight will be recorded on the Feeding Assessment case report form. We will use a digital scale

to determine all weight measurements. The weight per ml will be estimated based on the baseline measure and used to adjust the gross measure of intake by subtracting out spillage that occurred during the feed. We will calculate intake per feed from these measures less the amount spilled.

Spillage. We will account for spillage of milk by using a baby bib cloth for all feedings. Each caregiver-infant pair will be provided with a bib cloth for each observed feeding. The bib cloth will be weighed before and after each feed and the weights recorded on the Feeding Assessment form. The difference between the pre and post weights will be used as the measure of the amount spilled. A digital scale will be used and milk weight will be in grams. Spillage will be reported as a percent with the amount of milk in grams spilled/mopped up divided by the total amount of milk weighed in grams less the total amount of milk not used.

Caregiver Satisfaction. Our primary measure of caregiver's satisfaction will be the cup she prefers [secondary] and rated satisfaction [primary] which will be recorded in the In-Hospital Preference Survey completed after the caregiver has finished the feeding portion of the study (V5). A secondary measure will be what the caregiver reports uses most of the time measured in the Follow-up Survey 4 weeks post-discharge (V6). We will also measure the caregiver's satisfaction with each cup after each feeding measured in the Feeding Assessment and in the In-Hospital Preference Survey (V2-V5).

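### The sign test on caregiver preference ignores the randomised cup order; if order influences preference it loses power, and a sequence-stratified test avoids this at essentially no cost

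*Combined protocol and SAP*

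**What the plan says.** Section 3.1 assigns a crossover GEE to the feeding measures and a sign test to preference: "to assess intake, spillage, and feeding duration and a sign test to assess the" caregiver's preference. The level is given as "a two-sided p-value of 0.05 will be used". No sequence term is mentioned for preference.

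Section 3.0 says each pair uses both cups, "with the order of the cup used first and second randomized". Section 5.2.1 describes sealed, sequentially numbered envelopes and gives no allocation ratio or blocking.

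At Visit 3 (Section 5.1.3) the research assistant is to "Remove Cup 1 so it is not inadvertently or preferentially used over Cup 2". At Visit 5 (Section 5.1.5) the last Cup 2 feed is assessed and the preference survey is done; returning Cup 1 is listed after the survey. Section 5.2.2 says that satisfaction and preference "will be recorded in the In-Hospital Preference Survey completed after the caregiver has finished the feeding portion of the study (V5"). That sentence opens by calling these the primary measure, then tags preferred cup as secondary and rated satisfaction as primary. Caregiver satisfaction is a primary hypothesis in Section 2.2.

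Section 3.1 also plans an order check, comparing results for each cup between those who had it first and those who had it second. If design effects appear, second-cup data are dropped and the trial is analysed as a parallel-group comparison.

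**The concern.** At V5 the caregiver has just fed with Cup 2 and has been without Cup 1 since V3. Some of the preferences expressed may reflect which cup came last and not which cup is better. A sign test pools both sequences into one count of caregivers choosing the Nifty cup. Any order effect then enters that count as unmodelled structure, although the randomised sequence would allow it to be removed.

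The planned safeguard does not reach this endpoint. A preference needs experience of both cups, so no first-period version of it exists. If the order check is positive, the plan has no analysis of preference to fall back on.

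At stake is the efficiency of the preference analysis and, at a very uneven split, whether the result depends on which sequence happened to be larger.

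**Working it through.** **The plan's own figures.** Section 2.3 gives no power for a sign test. For 150 pairs and a 5% difference in either feeding measure it claims 90% power at alpha 0.05 without design effects, and 80% if carryover is observed, from a paired t-test with SD 11 and correlations 0.02 to 0.5. Reading the difference as 5 on the scale of that SD:
- Paired, N = 150: the SD of the difference is 11√(2(1−ρ)), i.e. 15.4 at ρ = 0.02 and 11.0 at ρ = 0.5. Power is 97.7% to 99.98%, so 90% is not reproduced (it is understated).
- First period only, 75 per sequence: 5/(11√(2/75)) = 2.78, power 79.5%. The 80% is reproduced.

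Neither figure bears on the sign test, and the mismatch is a separate matter.

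**Inputs.** From the documents: 150 pairs, two-sided 0.05, two sequences. Assumed: every caregiver states a preference; preference log-odds 0.5 (62.2% choose Nifty when order has no effect); recency log-odds r from 0 to 1.5. Among caregivers with no cup preference, r = 0.4 (0.405), 1.0 and 1.5 mean that 60%, 73% and 82% choose the last cup.

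**Model.** P(prefer Nifty) = expit(0.5 − r) if Nifty came first and expit(0.5 + r) if second. Under the null, 0.5 is replaced by 0, giving 0.5 − e and 0.5 + e.

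**Tests compared.**
- Exact two-sided sign test: with N = 150 it rejects when the Nifty count X is ≤ 62 or ≥ 88.
- Mainland-Gart: with a of n₁ Nifty-first pairs and b of n₂ medicine-cup-first pairs preferring their first cup, z = (a/n₁ − b/n₂)/√(p̄(1−p̄)(1/n₁+1/n₂)), uncorrected. Recency alone makes both proportions 0.5 − e, so it cancels.

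**Hand check, 75/75, r = 1.0.**
- Null: probabilities 0.269 and 0.731; mean of X 75; SD √(150 × 0.269 × 0.731) = 5.43, against √(150/4) = 6.12 assumed by the sign test. Size ≈ 2P(Z > 12.5/5.43) = 0.021.
- Alternative: probabilities 0.378 and 0.818; mean 89.6; SD 5.37. Power ≈ P(Z > (87.5 − 89.6)/5.37) ≈ 65%.

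**Exact enumeration, 75/75.**

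| r | Sign test size | Stratified size | Sign test power | Stratified power | Gap (points) |
|---|---|---|---|---|---|
| 0 | 0.041 | 0.055 | 83.9% | 86.6% | 2.7 |
| 0.4 | 0.037 | 0.055 | 81.3% | 85.4% | 4.1 |
| 1.0 | 0.021 | 0.049 | 65.6% | 76.7% | 11.1 |
| 1.5 | 0.008 | 0.051 | 39.4% | 65.5% | 26.1 |

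The 2.7-point gap at r = 0 owes nothing to order: it reflects the discreteness of the exact sign test and the uncorrected chi-square. Subtracting it leaves about 1.4, 8.4 and 23.4 points attributable to order.

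**Type I error at unequal splits.** With sizes n₁ and n₂, the null count has mean N/2 + e(n₂ − n₁) and variance N(0.25 − e²). Its mean squared deviation from N/2 is N/4 + e²[(n₂ − n₁)² − N], which exceeds the assumed N/4 only if |n₂ − n₁| > √150 = 12.2.

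| Split | Sign test size, r = 1.0 | r = 1.5 |
|---|---|---|
| 70/80 | 0.033 | 0.024 |
| 68/82 | 0.045 | 0.044 |
| 65/85 | 0.074 | 0.096 |

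The stratified test at 65/85 has size 0.049 to 0.050. Under simple 1:1 randomisation a split of 65/85 or worse has probability 0.12.

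**Averaged over splits.** Under simple 1:1 randomisation each caregiver's null probability is 0.5(0.5 − e) + 0.5(0.5 + e) = 0.5, independently of the others. The sign test's overall size is therefore 0.041 for every r.

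**Power at an uneven split, r = 1.0.** With 85 pairs Nifty-first and 65 Nifty-second, sign-test power is 34%; with the sizes reversed it is 89%. The stratified test gives 76% either way.

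**The case against.** The strongest objection concerns validity. A reader might infer that the sign test's level holds only with equal sequences and that any imbalance inflates type I error. The documents do not support that. Under simple 1:1 randomisation the test is exactly valid whatever the order effect. Even conditionally, 70/80 shows no inflation and 68/82 stays below 0.05. The 0.074 to 0.096 figures describe one unlikely realised split. Only systematic imbalance would inflate error overall, and no such imbalance is described. All of this stands. What remains is that the trial will be analysed at one known split, that Section 5.2.1 gives neither ratio nor blocking, and that pairs discharged before V5 drop out of the preference count, since Section 5.0 says participants are not kept in hospital to finish.

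Second, the recency effect is assumed. The survey timing makes it possible but says nothing about its size. At r = 0.4 the loss due to order is only 1 to 2 points. This stands, and it is why a range is shown.

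Third, preference is tagged secondary in Section 5.2.2, and the sample size was set on spillage and intake. A reader who sees satisfaction listed as a primary hypothesis might infer that a primary test is at fault; the tags put rated satisfaction in that place. This limits the weight of the point.

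Fourth, order is not wholly ignored, since Section 3.1 checks for it. That is true, but the remedy attached to the check cannot be used for a preference.

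**Conclusion.** The point holds as one of efficiency, with a conditional validity element. The preference analysis leaves out the factor the trial randomised, and the plan's order remedy does not fit this endpoint. With balanced sequences the sign test remains valid but becomes conservative as the order effect grows. At 150 pairs and preference log-odds 0.5, the power loss runs from about 4 points (recency 0.4) through 11 (1.0) to 26 (1.5), including about 3 points that exist without any order effect. Type I error rises above 0.05 only when a substantial order effect meets an imbalance clearly above 12 of 150. At such splits the sign test's power also depends on which sequence is larger.

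These sizes rest on the assumed preference and recency log-odds and on every caregiver stating a preference. If order has no effect, the sign test is valid and nearly as powerful. The point is worth correcting because the correction is cheap; it does not undermine the trial's primary analyses.

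**What to change.** In Section 3.1, replace the sign test with a sequence-stratified test of preference: Mainland-Gart (preferred first or second cup, by sequence), or the equivalent logistic regression with a sequence term. State how a caregiver with no preference is counted. Say explicitly that the rule of dropping second-cup data does not apply to preference.

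The cost is a few lines in the analysis plan. Cup order and stated preference are already recorded, so no new data are needed. If order has no effect, essentially no power is lost (86.6% against 83.9% at 75/75, the difference being a matter of test construction). Stating the allocation ratio and any blocking in Section 5.2.1 would also let a reader judge how uneven the sequences could become.

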5.0 Study procedures

Study participants will be asked to cup feed their infant with the generic cup and the Nifty Feeding Cup in the randomized order assigned. The caregiver will feed their infant with each cup at least 2 times before we measure feedings with the cup. Mothers will not be asked to exclusively cup feed during this study. Preterm infants started on cup feeding will typically start with a cup and then gradually transition to breastfeeding. Mothers are counseled to attempt breast feeding while their infant is using the feeding cup. Study procedures are aligned with KATH practice so the mother will not do anything different than what is clinically indicated as best for mother and baby.

Since infant participants are inpatients, the term ‘visit’ is meant loosely to indicate the sequential study activities that will take place. Research staff may check-in with the caregiver at any time during the participation in the study to coordinate study activities. The day and time of each study visit is an estimate but each visit will be completed before the next. To ensure the infant is clinically indicated to cup feed, prior to each feed we measure, the research assistant (RA) will consult with a provider to make sure the infant can be cup fed.

The caregiver will feed their infants the type of milk/formula in amounts determined by the clinical provider. The study team will not be involved in providing guidance regarding type of milk or amount recommended other than tracking it.

If the infant and/or caregiver have health, social or other problems that arise in the course of study participation that prevent either of them from participating in study visits, we will discontinue them from the study

Details of the tools (e.g. Surveys) and procedures (e.g. Feeding Assessment) used at each visit are outlined in Section 6 below. Also refer to the **Schematic of Study Procedures** found

immediately after the Protocol Summary and the **Visit Activities Schedule**, an Appendix to the protocol.

We estimate the RAs will each be able to manage a workload of 2-3 participants per week and that based on this rate, it will take about 1 year to complete enrollment and data collection activities.

Study participants will be discharged from hospital when clinically appropriate. Participants will not be retained in hospital to finish the study procedures.

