5.1 Visits

5.1.1 Visit 1. Baseline (Day 1, Hour 0)

After the consent process, the RA will conduct the Baseline visit. She will:

- Obtain the random assignment of which cup to introduce first
- Administer the Baseline Survey
- Measure the infant's current weight and length.
- Provide the caregiver with assigned Cup 1 and the instructions for use.

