5.1.2 Visit 2. Cup 1 Feed 1 (Day 1, >4 hours after V1)

To allow the caregiver time to feed her infant with Cup 1 for at least two times without being observed by the RA, we will conduct this visit >4 hours after V1. The RA will periodically check in to see if at least two feedings have occurred and then conduct V2. During Visit 2, the RA will:

- Conduct the Feeding Assessment

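### Section 3.1 leaves open whether the GEE for spillage adjusts for feed counts that build up after the cup is issued. Keep those counts to a labelled sensitivity model, and adjust the first-cup-only fallback for baseline variables.

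*Combined protocol and SAP*

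**What the plan says.** Section 3.1 analyses intake, spillage and feeding duration by GEE for a crossover. Its covariate list is permissive and open-ended. It includes "number of prior cup feeds with assigned cup, and number of cup feeds between measured feedings", along with the amount of earlier feeding and the nutrition type. No primary covariate set is fixed, and no covariate is assigned to a sensitivity analysis. The same section says the analyst will be blinded to cup assignment.

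Timing comes from Sections 3.0 and 5:

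- Cup 1 is issued at V1: "Provide the caregiver with assigned Cup 1 and the instructions for use". Cup 2 is issued at V3.
- Two unobserved feeds is a minimum: "The RA will periodically check in to see if at least two feedings have occurred and then conduct V2". V4 follows the same rule. Visits have lower time limits only (more than 4 hours, more than 2 hours).
- Feeds between the two measured feeds of a cup may or may not happen (5.1.3, 5.1.5).
- Exposure is approximate: "Each caregiver/infant pair will use the Nifty Feeding Cup for about 24 to 36 hours", and likewise for the generic cup.
- Cup feeding is not exclusive: "Mothers will not be asked to exclusively cup feed during this study".
- Milk is set clinically: "The caregiver will feed their infants the type of milk/formula in amounts determined by the clinical provider".

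Most of the usual covariates, such as maternal age, "will not be included because the comparison is the same caregiver/infant pair". If design effects are seen, the plan falls back on a comparison by first cup, "dropping the data from the second cup and removing the cross over design from our study".

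**The concern.** Randomisation protects the comparison of spillage by assigned cup. It does not protect a comparison made at equal values of something that happens after assignment. Both feed counts happen after assignment.

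If one cup leads to more or fewer cup feeds before the measured feed, adjustment does two things. It removes any part of the cup effect that works through practice. It also opens a path through shared causes of count and spillage, such as the infant's feeding ability that day. The plan makes both routes conceivable: Sections 1.3 and 2.2 expect the cup to change duration and intake, and Section 2.3 treats learning as able to affect outcomes. Because the list is open, whether the primary estimate is the total effect of the assigned cup is settled only at analysis.

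The second matter is smaller. The same-pair argument for leaving out baseline covariates is sound for the within-pair analysis. The first-cup-only fallback compares different pairs, so the argument does not carry over.

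**Working it through.** **1. The plan's own figure.** Section 2.3 states 80% power for a 5% difference if carryover is observed. Inputs: 150 pairs, an assumed 75/75 split, SD 11 (unit not stated, read here as points), two-sided alpha 0.05. The standard error is 11 × √(2/75) = 1.796, so the noncentrality is 5/1.796 = 2.784 and two-sample t power is 79.0%. The stated figure reproduces.

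**2. Baseline adjustment of the fallback.** Replace 11 by 11 × √(1 − R²). The documents give no R², so a range is shown.

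| R² | Residual SD | Power, 75 per arm | Power, 100 per arm |
|---|---|---|---|
| 0 | 11.0 | 79.0% | 89.2% |
| 0.1 | 10.4 | 83.0% | 92.1% |
| 0.2 | 9.8 | 87.1% | 94.7% |
| 0.3 | 9.2 | 91.1% | 96.9% |

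**3. Direction of bias from the counts.** Let the cup shift the count by a feeds. Let day-level feeding ability (SD 1, correlation ρ between periods) shift the count by b and lower spillage by c points, with residual count SD 1. For one feed per cup, regressing the within-pair spillage difference on the count difference gives

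bias = a·b·c·(1 − ρ) / (1 + b²(1 − ρ)).

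It is zero if a = 0. For c > 0 its sign is the sign of a·b, so it depends on whether the cup raises or lowers counts and on whether abler infants have more or fewer cup feeds. The documents settle neither. This formula ignores the two-feed minimum, so it is used for direction, not size.

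**4. Size, respecting the design.** All inputs are assumed.

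- Count before the first measured feed: 2 + a·cup + b·U + noise (SD 1), rounded, never below 2.
- Feeds between measured feeds: 0.5a·cup + 0.5b·U + noise (SD 0.7), rounded, never below 0.
- Count before the second measured feed: first count + 1 + feeds between.
- Spillage: 20 − 5·cup − c·U + pair term (SD 6) + residual (SD 7).
- a = 0.5 or 1; (b, c) = (0.5, 3) or (1, 6), with either sign of b.
- Exchangeable GEE with cup, period, sequence and feed number, with and without the two counts. 100,000 simulated pairs, standard errors scaled to 150.

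After the minimum is applied, the mean cup difference in count is about 0.4 to 0.8 feeds.

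| ρ | Bias if abler infants have more cup feeds | Bias if they have fewer |
|---|---|---|
| 0 | +0.5 to +2.5 | −0.5 to −2.5 |
| 0.5 | +0.4 to +2.0 | −0.4 to −1.9 |
| 0.8 | +0.3 to +1.5 | −0.3 to −1.5 |

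Positive means that the 5-point benefit is understated. If the cup lowers counts the signs swap, and the sizes are about 0.2 to 1.8 because the minimum holds the counts up. Without the counts, every estimate lay within 0.1 of −5.

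**5. No shared cause, practice only.** If each extra feed lowers spillage by 0.5 to 1 point, the total effect is −5.2 to −5.8 and the adjusted estimate is about −5.0. The two models answer different questions.

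**6. Cup does not change counts (a = 0).** Bias is zero. The standard error goes from 0.67 to 0.65 (b = 0.5, c = 3) or from 0.89 to 0.78 (b = 1, c = 6) at ρ = 0. At ρ = 0.5 it stays at 0.62 or goes from 0.75 to 0.71. At ρ = 0.8 it is essentially unchanged.

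**7. Why the first-versus-second check is left alone.** Assume a pure 3-point period effect, no carryover, and 75 v 75. The noncentrality is 3/1.796 = 1.67, so the check flags 38% of the time per cup. With R² of 0.1 to 0.3 it flags 42% to 51%.

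**The case against.** The adjustment is optional, and nothing in the documents shows that the cup changes feed counts. Provider-set milk amounts and the research assistant's check for two feeds before V2 and V4 may keep counts similar. If so, adjustment does no harm and may help slightly. This stands, and it makes the point conditional. A reader might infer that the planned analysis is biased, or biased in favour of one cup. The documents support neither: the adjustment is not mandated, and the direction depends on two unknown signs.

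Analyst blinding limits choosing a model by its result. That also stands, but blinding does not turn an estimate conditioned on a post-assignment count back into the total effect.

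On the fallback, the first-cup comparison is randomised and valid unadjusted, and it already gives close to the stated 80%. The text leaves out most covariates rather than all, so baseline adjustment is not forbidden. Correct: the gain is precision only, and its size rests on an assumed R².

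One might extend baseline adjustment to the first-versus-second check, since it too compares different pairs. That check cannot separate a period (learning) effect from carryover. Sharpening it makes an ordinary period effect more likely to lead to all second-cup data being discarded.

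**Conclusion.** The point holds in conditional form. Section 3.1 names two post-handover counts as candidate covariates for a primary outcome and does not fix the model. If the cup leaves counts unchanged, the cost is nil and there may be a small gain in precision. If it changes them, the adjusted estimate departs from the total effect by an unknown amount: about 0.3 to 2.5 points either way for an assumed shift of 0.5 to 1 feed (before the minimum is applied) and an assumed 5-point effect. Only the model without the counts is safe in both cases. Whether the earlier-feeding and nutrition covariates share the problem cannot be told, because the text does not say when they are measured and the form is a separate attachment.

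For the fallback, the stated reason for omitting baseline covariates does not apply. The loss is precision: 79% power against 83-91% at 75 per arm, if SD 11 is in points and V1 variables explain 10-30% of the variance. A claim that the fallback is invalid would go too far. This should be changed before analysis; it is not a demonstrated error in the result.

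**What to change.** Replace the open covariate list in Section 3.1 with a fixed rule:

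- **(a)** The primary GEE contains cup, period, sequence and feed number, and no covariate measured after handover of the cup being assessed.
- **(b)** The two feed counts go only into one labelled sensitivity model, described as a contrast at equal practice. The earlier-feeding and nutrition covariates join them if they are measured after handover.
- **(c)** The first-cup-only fallback adjusts for named V1 variables already collected, for example infant weight, gestational age and age at enrolment. Do not apply this to the first-versus-second check.

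Cost: wording only, no new data. The primary model may be slightly less precise if the cup does not change counts, and the fallback carries a few extra parameters.
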